NCT05166356

IRB# 21-007898

Describing the Determinants and Effects of Variation in the Adoption a Use of the NOHARM Pain Management Intervention Among Diverse Surgical Practices

September 11, 2023 V8

IRB Minimal Risk Protocol Template

General Study Information

Principal Investigator: [name], MSCE

Study Title: Describing the Determinants and Effects of Variation in the Adoption a Use of the NOHARM Pain Management Intervention Among Diverse Surgical Practices

Protocol version number: September 11, 2023 Version 8

Research Question and Aims

Background and Introduction

NOHARM (Non-pharmacologic options in post-operative and hospital-based rehabilitation and pain management pragmatic trial) is a National Institutes of Health (NIH)-funded pragmatic trial testing whether patient education about non-pharmacologic pain management options, coupled with support from ambulatory and inpatient surgical care teams, improves pain and function while avoiding opioid overuse in the post-operative setting. This trial is currently being conducted among diverse surgical practices across the Mayo Clinic Enterprise as part of a stepped wedge, clusterrandomized pragmatic trial (IRB# 20-004839) with the implementation scheme depicted below (see Figure 1).

Figure 1: Surgical	practices in the NOHARM Trial
--------------------	-------------------------------

	Tranche 1 Rochester Cardiac, C-Section Florida Ortho Eau Claire Ortho, Colorectal, Gyn, C-section LaCrosse Gyn, C-Section	Tranche 2 Rochester Ortho, Gyn, Lung Arizona Lung, Cardiac Mankato Colorectal	Tranche 3 Rochester Colorectal Florida Transplant Arizona Colorectal, Gyn, Transplant	Tranche 4 Florida Colorectal, Gyn, Lung, Cardiac Eau Claire Lung, Cardiac Mankato C-Section	Tranche 5 Rochester Transplant Arizona Ortho Mankato Ortho LaCrosse Ortho, Colorectal
condition	Data Collection 10/16/2020				
Step 1	Go live 3/1/2021				
Step 2		Go live 10/1/2021			
Step 3			Go live 5/1/2022		
Step 4				Go live 12/1/2022	
Step 5					Go live 7/1/2023

As part of the NOHARM trial, all patients on the NOHARM registry (e.g. patients in all active clusters undergoing a qualifying procedure) receive an educational tool in their portals pre-operatively called the Healing After Surgery Guide. Ambulatory care teams are encouraged to inform patients about the Guide and encourage patients to access it. Patients are expected to review the guide and select their non-pharmacologic preferences from among 13 options. These selections automatically populate flowsheet rows in Epic and trigger other supports that prompt inpatient nurses to provide tailored education and the selected modalities as feasible. This trial is operating under a waiver of consent as previously approved by the Mayo Clinic IRB.

The ongoing NOHARM study is designed to determine the effectiveness of the NOHARM intervention (e.g. the patient education and clinical decision making and support bundle). Inevitably, the NOHARM intervention will be more effective in some practices and for some patients than in others. Reasons for this are multiple and complex, but important to understand. For example, if care teams within a surgical practice do not deliver the NOHARM intervention as intended it may appear less effective than it could be. Similarly, the same effect could be seen if patients are unable or unwilling to participate in the intervention fully. The ongoing NOHARM study is not designed to explore or make sense of these issues. Thus, it is unable to explain variation in key effectiveness outcomes. More importantly, the trial itself is unable to provide practical guidance on how to optimize the intervention to improve its potential for adoption and use by diverse surgical care teams and types of patients.

Study Objective and Aims

The objective of this follow-on study is to enrich the ongoing NOHARM pragmatic trial initiative with a mixed methods analysis of patient and care team factors that affect the routine adoption, implementation, and meaningful and sustainable use of the NOHARM intervention. To accomplish this objective, we will pursue the following aims:

Aim 1: Explore differences in patient engagement with the NOHARM intervention, use of non-pharm modalities, and clinical outcomes by key patient demographics, including surgical procedure type, gender, and opioid abuse risk. This aim will provide information about patient characteristics that may better predict who will use and/or benefit from the NOHARM intervention and who will not.

Aim 2: Qualitatively explore patient-level factors contributing to their ability to effectively engage with the NOHARM intervention in a diverse subgroups that adopt and use the intervention as intended and those that do not, respectively. This aim will provide information that helps us explain *why* some patients tend to use and/or benefit from NOHARM and others do not.

Aim 3: Characterize, using mixed methods, the relative fidelity and sustainability of implementation of NOHARM among surgical practices and test for associations with patient engagement and clinical outcomes. This aim will provide information about the characteristics of care teams that tend to adopt and maintain use of the NOHARM intervention and those that do not. It will also provide information about whether care teams play an important role in prompting patients to engage with and benefit from the NOHARM intervention.

Participants

Participants eligible for this study will be patients on the NOHARM trial registry (e.g. patients that were automatically assigned to receive the NOHARM intervention as part of their surgical care) and/or their charts and members of their care teams, including nurses, doctors, physical therapists, nurse practitioners and physician assistants, and medical assistants.

Aim 1 will exclusively use existing, Epic-based datasets and reports to conduct passive, observational secondary analyses using existing variables from medical record. For this aim, no participants will be directly contacted. For Aims 2 and 3 we will use qualitative methods and will recruit a purposeful sample of patient and care team member participants, respectively. Details about these procedures and samples are outlined below.

Procedure and Methods

Aim 1: Explore differences in patient engagement with the NOHARM intervention, non-pharm modalities, and clinical outcomes by key patient demographics, including surgical procedure type, gender, and opioid abuse risk.

We will create Epic reports that combine all key variables for this aim. Specifically, reports will list all patients on the NOHARM registry, along with their age, sex, procedure type, surgeon, surgery location, insurance type, home zip code (for rurality), portal status (user vs non-user) and whether the patient interacted with the Healing After Surgery Guide. For patients that interacted with the Guide, the reports will also include opioid abuse risk (calculated from patient-reported outcomes) and non-pharm selections made, if any. Finally, reports will also include non-pharm modalities used as self-reported in post-operative surveys and include all patients that have completed the post-op follow-up period.

We will construct a "patient engagement and fidelity" variable based on data existing in the reports (made nonpharm selections y/n, used non-pharm modality in recovery y/n) and calculate these for all patients. We will use the distribution of patients by this variable to assess for correlations with clinical outcomes collected in the NOHARM trial (e.g. changes in pain and function). We will also explore the distribution of the variable within different demographic subgroups. If important contributors to patient engagement and fidelity are identified by this process, we will conduct adjusted analyses as appropriate.

Aim 2: Qualitatively explore determinants of patients' ability to effectively engage with the NOHARM intervention in a diverse subset of patients that adopt and use the intervention as intended and those that do not, respectively.

Patient Interviews: In Aim 2, we will contact, consent, and purposively interview up to 64 patients. We will aim to distribute participants across the 32 clinical practices involved in NOHARM (approximately 2 per practice). We will identify potential participants from reports of NOHARM patients (see Aim 1) and contact them via telephone, email, and or postal mail (contact info obtained from chart) with invitation to participate in a single, 30-minute, recorded telephone or Zoom-based interview. We will collect written HIPAA authorization for patients as part of this consenting process. If the subject is agreeable, documentation of HIPAA authorization will involve the use of Electronic Informed Consent (otherwise referred to as Docu-Sign) for HIPAA authorization forms. This is an institutionally approved process for documenting consent/HIPAA authorization using an on-line process. The subject may print or electronically save the consent form, or may contact the study team to provide a copy of the consent. If the subject prefers not to use Electronic Informed Consent, the study team will utilize a paper form for enrollment of these subjects, either via mail or in-person. We will compensate interviewees for their time with \$20 in remuneration. We will conduct interviews throughout the project period, spreading them out amongst currently active practices. All interviews will be semi-structured and led by a guide that focuses on 1.) understanding the patient's experience with the intervention, 2.) exploring the predisposing, reinforcing, enabling, and environmental factors that cause variation in engagement and fidelity within groups and, 3.) potential strategies for improving it. It is possible that we will not be able to recruit representative patients within all 32 surgical practices, but we will aim to recruit at least 6 patients for each of the 7 surgical

disciplines (e.g. not necessarily 2 patients from each discipline and location) across the entire sample (at least 42 total interviews throughout the study duration). We will transcribe all recordings for analysis. We will first use a rapid analytic approach to analyze transcripts by summarizing each interview transcript under domain labels, corresponding to the interview questions. Individual summaries will be compiled into a Data Matrix to allow for comparison across interviews and identify emergent themes and differences between groups of patients, who vary in their level of engagement with the NOHARM intervention. The Rapid approach allows for ongoing learning and quick identification of any iterative improvements that could enhance the intervention for patients. The final data matrix may be uploaded to Nvivo to allow for coding and querying of codes, followed by memo summarization and discussion to arrive at consensus of themes.

Once data has been rapidly analzyed, we may return to the transcripts for more in depth analysis consisting of regular meetings, code book drafting and revision, coding of transcripts, resolving differing interpretations by consensus, running coding queries in Nvivo, memo summarization, and subsequent synthesizing into themes. We will categorize themes that characterize and distinguish high and low fidelity NOHARM engagement within and between patient groups, and may explore other key topic areas that emerge upon reviewing the qualitative data.

Aim 3: Characterize, using mixed methods, barriers and facilitators to implementing the NOHARM intervention and its potential for sustainability among surgical care teams and test for associations with patient engagement and clinical outcomes.

This aim will provide information about barriers and facilitators to implementation of NOHARM experienced by different clinical care team members (e.g., nurses, nursing leadership, physical and occupational therapy, physical and occupational therapy leaders). Data gleaned from this aim may help us understand whether care teams play an important role in prompting patients to engage with and benefit from the NOHARM intervention.

Inpatient Care Team Interviews

To understand barriers and facilitators to implementation and adoption of the NOHARM intervention by inpatient care teams, we will conduct interviews with at least 1, but up to 2-3 key inpatient stakeholders from each surgical practice at least three months after their practice's go-live. We will conduct between 32 (1 interview per practice) and 96 (3 interviews per practice) interviews in total.

We will recruit participants to these interviews via email-based invitations to clinical stakeholders with whom we already have relationships (e.g., nursing managers, nursing education specialists, clinical nurse specialists, and charge nurses). These video-based interviews will last 30-45 minutes and be semi-structured to gather data corresponding to the 5 Consolidated Framework for Implementation Research (CFIR) 2.0 domains: 1) innovation characteristics, 2) outer setting, 3) inner setting, 4) key roles and characteristics, and 5) implementation process. We will make adaptations to the interview guide as needed to explore salient topics. All participants will provide verbal consent to participate. Participants will receive \$50 remuneration for participating in the interview, which will be given via payroll. All audio recordings will be transcribed and de-identified.

Analysis:

We will use a rapid analysis approach to summarize transcripts by summarizing each interview transcript under domain labels, corresponding to the interview questions. Individual summaries will be compiled into a Data Matrix to allow for comparison across practices and identify emergent themes. Using a rapid analytic approach will allow us to share ongoing findings at team meetings so that findings may be used to refine intervention implementation for later tranches. The data matrix domains may later be mapped back to to the CFIR constructs or domains the questions were designed to address so that emergent themes can be organized using the CFIR model. Constructs may also be assigned a numeric, valence rating for each practice to determine the strength of different barriers and facilitators across practices.

Once data has been rapidly analyzed, we may return to the transcripts for more in depth analysis consisting of regular meetings, code book drafting and revision, coding of transcripts, resolving differing interpretations by consensus, running coding queries in Nvivo, memo summarization, and subsequent synthesizing into themes. This will enable a more in-depth assessment of the barriers and facilitators to implementation practices experienced.

Inpatient Stakeholder Surveys

We will also give inpatient stakeholders the opportunity to share feedback on their thoughts about the intervention via a short survey consisting of mostly multiple choice questions, which should take approximately 5 minutes to complete. The survey will ask about stakeholders' role and Mayo Clinic site they work at, which will allow us to agreggrate data at the site level, but will maintain the anonymity of individual's responses. We will ask stakeholders' about their impressions about the added value and burden of the intervention, to what extent they have encouraged their staff to support the intervention, and to what extent they would like to see the intervention become part of practice. These survey responses will help us understand to what extent inpatient allied health nursing leaders (e.g., nurse managers, interim nurse managers, clinical nurse specialists, nursing education specialists) at different sites support the intervention, which is likely to impact staff's uptake of the intervention and impact staff intervention fidelity.

We will recruit inpatient allied health nursing leaders (e.g., nurse supervisors, nurse managers, interim nurse managers, clinical nurse specialists, nursing education specialists) from all 32 clinical practices participating in the trial. We will recruit up to 90 allied health nursing leaders. Nursing leaders may be recruited in person by members of our implementation team and given the opportunity to complete the survey and turn it in in person or mail back to our team via intra-clinic mail, depending on what they prefer. For those who complete the survey online, we will email them an invitation to complete the survey along with an embedded link to complete the online version (created using Qualtrics or RedCap). Completion of the survey will be taken as a form of assent. Nursing leaders may also be recruited by phone and asked to provide answers to the survey questions via a short (< 7 minute phone call) that the study team member records in the web-based database housing the survey (e.g., RedCap, Qualtrics). Those who complete the survey will receive remuneration in the form of \$35 added to their paycheck, to compensate busy nursing leaders for their time.

Analysis:

All paper survey responses will be entered into the web-based platform (Qualtrics or RedCap) used to collect responses from the web-based version of the survey for those who choose to complete the survey online. We will calculate descriptive statistics from this survey at the site level (e.g., Rochester, Arizona, Florida, Eau Claire, La Crosse, and Mankato). The survey responses will help us identify sites who's leadership is more or less enthusiastic about the intervention and the prospect of the intervention being sustained in some form upon study determination. These findings will complement findings from the stakeholder surveys that seek to identify specific barriers and facilitators to implementation of the intervention on inpatient nursing units.

Inpatient Epic Reports:

Using procedures like those of Aim 1, we will create automated Epic reports that summarize care team fidelity to the NOHARM intervention. Specifically, we will use these reports to identify the proportion of NOHARM patients who are discharged from a practice with NPPC selections documented in flowsheet rows and the proportion of patients for which at least some of the Healing After Surgery education listed in the Education Tab has been delivered. We will then rank order practices based on the proportion of patients who did not have NPPC selections in their chart at the time of surgery, but were discharged with NPPC selections, and the proportion of patients who had at least some Healing After Surgery education delivered by the time of discharge to identify the top 10 and bottom 10 performing practices interviewed. The proportion of patients discharged with NPPC selections is a good proxy for inpatient care team fidelity because this data point can be reliably captured and Healing After Surgery education points auto-populate for all patients, so we can evaluate whether they have been completed or not.

Analysis: After, we have identified the practices with the highest and lowest fidelity, we will create a new data matrix with the qualitative interview data from the 10 highest and lowest fidelity practices and identify differences in themes between the highest and lowest performing practices organized according to CFIR constructs. We will also compare the CFIR construct ratings between high and low fidelity sites to determine whether ratings (perceived barriers and facilitators pertaining to the different constructs) differentiate inpatient practices with high verus low fidelity.

Physical and Occupational Therapy

To understand barriers and facilitators to implementation and adoption of the NOHARM intervention by physical and occupational therapy teams, we will administer an anonymous web-based survey (RedCAP). The survey will take approximately 10 minutes to complete and consist of multiple-choice questions along with a few open-ended questions for therapists to provide additional feedback if they wish. We will ask staff which Mayo Clinic location they work at, but no other identifying information will be collected.

We will recruit physical and occupational therapists, by working with therapy leaders and requesting ~15 minutes on standing therapy meetings (~2 minutes to introduce the survey and ~10-13 minutes to allow time for survey completion). After introducing the survey, we will share the link to the survey in the chat so that staff who are interested in completing the survey can do so. Paper copies may also be supplied for in person meetings. For therapy leaders who prefer not to offer the opportunity to participate during a staff meeting, we will ask them to distribute an email invitation inviting staff to participate in the survey, which will contain the survey URL. We will ask that leaders share meeting attendance or staff distribution lists with our team so we can calculate a response rate, but due to the anonymous nature of the survey, we will not be able to identify which staff member chose to participate and who did not. We seek to recruit a total of n = 280 therapists.

Epic Reports: To distinguish between high and low fidelity therapy practices, we will pull Epic report data on therapists' interaction with the NOHARM therapy identifier (BPA=Best Practice Advisory) and use of the NOHARM therapy smartphrase within their documentation. We will then rank order therapy practices from highest to lowest fidelity according to the frequency by which therapists acknowledge the NOHARM BPA and the frequency with which therapists documented supporting the patient's NOHARM non-pharmacologic pain care preferences during their therapy sessions, using the NOHARM therapy smart phrase.

Analysis: We will explore differences in survey responses between high and low fidelity therapy practices identified by the Epic reports to determine whether certain barriers or facilitators were more common amongst high or low fidelity practices.

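### Aim 1 offers information on who benefits from NOHARM, but its data hold only patients assigned to it, so outcome differences mix recovery with effect

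*Protocol*

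**What the plan says.** Under Study Objective and Aims, the protocol says Aim 1 will give information about "patient characteristics that may better predict who will use and/or benefit from the NOHARM intervention and who will not". The aim statement and the Aim 1 heading under Procedure and Methods both include differences in clinical outcomes by procedure type, gender and opioid abuse risk among the things to be explored.

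The source of patients is fixed in three places:

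- Background and Introduction describes the registry as "patients in all active clusters undergoing a qualifying procedure", all of whom are sent the Guide.
- Participants describes registry patients as "patients that were automatically assigned to receive the NOHARM intervention as part of their surgical care".
- Procedure and Methods, Aim 1, builds its reports from the registry. It forms an engagement and fidelity variable from two yes/no items (selections made; a modality used in recovery), correlates it with the parent trial's clinical outcomes and examines it by demographic subgroup. Adjusted analyses follow only if important contributors to engagement are found.

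The idea of benefit recurs. Background and Introduction states: "Inevitably, the NOHARM intervention will be more effective in some practices and for some patients than in others". It says of the parent trial: "Thus, it is unable to explain variation in key effectiveness outcomes". Aim 2 seeks to explain why "some patients tend to use and/or benefit from NOHARM and others do not". Aim 3 asks about the care team's role in "prompting patients to engage with and benefit from the NOHARM intervention", and the Aim 3 text under Procedure and Methods repeats this with a further hedge.

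**The concern.** To say that one kind of patient benefits more than another is to say that the effect of NOHARM differs between them. That requires, for each kind of patient, some information on outcomes without NOHARM. The Aim 1 data set contains none.

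Patients having different operations can be expected to recover differently whatever pain education they receive, and the same may hold for other characteristics. A group that recovers well under any care could be reported as benefiting. A group that recovers poorly but gains from NOHARM could be reported as not benefiting. Since the study is meant to guide how the intervention is improved and for whom, that guidance could be aimed at the wrong patients.

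**Working it through.** The protocol gives no sample size, power or effect figure for Aim 1, so there is no stated number to reproduce. The check is one of identification.

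**1. Outcomes by patient characteristic.** For subgroups A and B, let R be the mean outcome without NOHARM and E the effect of being assigned it. Assigned patients show only Y = R + E. The observed difference is

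D = Y_B − Y_A = (R_B − R_A) + (E_B − E_A).

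The difference in benefit is the second bracket. The data give D, and nothing in them separates the two brackets.

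**2. Illustration** (assumed values, none from the protocol; points of pain reduction).

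- Subgroup A: R = 3, E = 0, so Y = 3.
- Subgroup B: R = 1, E = 1, so Y = 2.
- D = 2 − 3 = −1. A looks 1 point better, although only B benefits.

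Now hold the true benefit difference (B minus A) at +1 and vary A's recovery advantage:

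| A's recovery advantage | Observed B − A | True benefit difference |
|---|---|---|
| 0 | +1 | +1 |
| 1 | 0 | +1 |
| 2 | −1 | +1 |

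The sign of the observed difference does not settle the sign of the difference in benefit. Change scores do not help, because R is then the change that would have happened anyway, and that too can differ between subgroups.

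**3. Engagement and outcome.** Engagers and non-engagers were all assigned NOHARM, so their contrast cannot show the effect of being assigned it. At most it could inform the effect of engaging, and only if no unmeasured trait drives both engagement and recovery. One of the two engagement items, use of a modality in recovery, is itself measured after surgery.

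For scale, suppose engaging has no effect and one trait, the only link between the two, correlates 0.1 to 0.3 with both engagement and outcome (assumed). The induced correlation is r = 0.1 × 0.1 = 0.01 up to 0.3 × 0.3 = 0.09. With a proportion p engaging, the mean difference in outcome SDs is r / √(p(1 − p)):

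- p = 0.5: 0.01/0.5 = 0.02 up to 0.09/0.5 = 0.18.
- p = 0.3: 0.01/0.458 = 0.02 up to 0.09/0.458 = 0.20.

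Engagers would appear 0.02 to 0.20 SD better with no effect at all. This shows direction, not an expected size.

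**4. Predicting use.** Engagement and use are observed directly in assigned patients, so no unassigned comparator is needed. There is a separate limit: the Aim 1 reports carry opioid abuse risk only for patients who interacted with the Guide. It is absent for all who did not, so it cannot predict interaction. Among those who did interact, it can still be related to selections made or modalities used.

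**The case against.** The strongest reply is that this is a matter of wording in a hedged sentence. Aim 1 explores; it offers information on characteristics that may predict; it is labelled observational; and its outcome analysis is described as correlation. The detailed methods relate engagement to outcomes and engagement to subgroups. They set out no analysis that ranks subgroups by benefit. The study's stated objective is adoption, implementation and use, with effectiveness left to the parent trial. The examples of uneven effectiveness in Background and Introduction concern teams not delivering the intervention and patients not taking part, both of which can be seen among assigned patients. Details of adjustment may also sit in an analysis plan that is not shown.

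Much of this stands, and it keeps the point minor. It does not remove it. The aim names benefit as a target, and its statement and heading call for outcomes by characteristic. Eligibility and data source are fixed in this document, so an analysis plan working within them has no unassigned group to use, and adjustment cannot create one. Both descriptions of the registry are introduced by e.g., but each reads as a definition, and nothing in the Aim 1 methods adds patients from before go-live.

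A reader might infer more: that Aim 1 as a whole fails, or that every mention of benefit fails for the same reason. The document does not support that. Describing engagement and use is what most of Aim 1 does, and it stands. Aim 2 consists of interviews, to which the decomposition of quantitative subgroup differences does not carry over. In Aim 3 the later text says only that the data "may help us understand whether care teams play an important role in prompting patients to engage with and benefit from the NOHARM intervention".

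**Conclusion.** The point holds as a minor one. As written, Aim 1 offers information on who benefits from data that can show only who uses NOHARM and how assigned patients fare. The conclusion rests on one reading, that the registry holds only patients assigned the intervention, and on no numerical assumption. The size of any misreading cannot be given, because it depends on recovery differences that the protocol does not state; the figures above only illustrate direction.

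It would go too far to say that the protocol plans a test of effect modification, or that it was bound to use the parent trial's patients from before go-live. It plans no such test, and it does not establish that the same characteristics and outcomes were recorded in those patients. Nor is prediction of use wholly untouched: the restriction on opioid abuse risk is a real, separate limit on one of the three characteristics that Aim 1 names.

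**What to change.** - In Aim 1, limit the claim to who engages with or uses NOHARM.
- Add one reporting rule: outcome differences by characteristic, and engagement-outcome correlations, are reported as descriptive or prognostic among assigned patients, not as benefit.
- Relate opioid abuse risk only to selections or modality use among patients who interacted with the Guide, and say that it cannot predict that interaction.
- Where Aim 3 relates care-team fidelity to outcomes, both in the aim statement and under Procedure and Methods, describe the result as association. A matching change in Aim 2 is optional.

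The cost is a few sentences, with no new data or patients.

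If the team wants to address benefit itself, an optional analysis would estimate characteristic-by-intervention interactions in the parent stepped-wedge data, including patients from before go-live and adjusting for practice and calendar period. It is possible only for characteristics and outcomes recorded in both conditions, which would have to be confirmed first. It would need a protocol modification and a further data extract from the parent trial, which runs under its own IRB number.

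### The Aim 1 reports list no surgery date, so pooled procedure-type comparisons, chiefly those involving transplant and to a lesser degree lung, can be mixed with rollout timing

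*Protocol*

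**What the plan says.** Aim 1 (Protocol, Study Objective and Aims) compares engagement, modality use and "clinical outcomes by key patient demographics, including surgical procedure type, gender, and opioid abuse risk". The Aim 1 methods state: "We will create Epic reports that combine all key variables for this aim". The list that follows says that "reports will list all patients on the NOHARM registry, along with their age, sex, procedure type, surgeon, surgery location, insurance type, home zip code", and adds portal status, Guide interaction, opioid abuse risk, selections made and self-reported modality use. Surgery date, calendar step and time since go-live are not on it. No calendar window is set either: the reports "include all patients that have completed the post-op follow-up period".

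The engagement variable is built from these reports, correlated with the trial's clinical outcomes, and examined by subgroup: "We will also explore the distribution of the variable within different demographic subgroups". Adjusted analyses are to follow if this process turns up important contributors.

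Registry membership (Background and Introduction) means "patients in all active clusters undergoing a qualifying procedure", so each practice contributes patients from its go-live on. Figure 1 staggers go-live over five tranches, from 3/1/2021 to 7/1/2023. On possible change over time, the Aim 2 interview analysis says: "The Rapid approach allows for ongoing learning and quick identification of any iterative improvements that could enhance the intervention for patients". The analysis paragraph under Inpatient Care Team Interviews (Aim 3) adds that findings may serve to refine implementation in later tranches.

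**The concern.** Procedure type is the first comparison factor that Aim 1 names, and the aim is meant to show who will use or benefit from the intervention. Procedure types did not enter the rollout evenly. If engagement changes over calendar time, or as a practice gains experience after go-live, a pooled comparison of procedure types carries part of that change. The engagement-outcome correlation is open to the same mixing if both quantities drift.

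The stated adjustment rule does not protect against this. It responds to contributors found from the listed data, and a list without a patient-level date cannot show time to be one. The risk is that a procedure type is reported as a predictor of use, or of non-use, when part of the difference comes from when its practices were observed.

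**Working it through.** **Reproducing the plan's count.** Figure 1 gives 9 + 6 + 5 + 7 + 5 = 32 practices in 7 disciplines, which agrees with the 32 practices and 7 disciplines stated under Aim 2. Each location-procedure pair occurs once, so practice, tranche and go-live date can be derived from two listed fields.

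**Spread over the rollout.** The first four steps last 7 months each. Assumptions: equal volume per practice and a fifth step of 7 months (to the end of January 2024). A practice in tranche k is then active for 6 − k steps. Steps 1-2 are the time before 5/1/2022.

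| Type | Practices in tranche 1/2/3/4/5 | Active practice-steps | Of these in steps 1-2 | Share |
|---|---|---|---|---|
| C-section | 3/0/0/1/0 | 3×5 + 2 = 17 | 3×2 = 6 | 35% |
| Ortho | 2/1/0/0/3 | 2×5 + 4 + 3×1 = 17 | 2×2 + 1 = 5 | 29% |
| Gyn | 2/1/1/1/0 | 2×5 + 4 + 3 + 2 = 19 | 2×2 + 1 = 5 | 26% |
| Cardiac | 1/1/0/2/0 | 5 + 4 + 2×2 = 13 | 2 + 1 = 3 | 23% |
| Colorectal | 1/1/2/1/1 | 5 + 4 + 2×3 + 2 + 1 = 18 | 2 + 1 = 3 | 17% |
| Lung | 0/2/0/2/0 | 2×4 + 2×2 = 12 | 2×1 = 2 | 17% |
| Transplant | 0/0/2/0/1 | 2×3 + 1 = 7 | 0 | 0% |

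The total is 103 practice-steps. If data end instead at the version date, 11 September 2023, the C-section and transplant shares are 42% and 0%. Mean surgery dates then fall 16.2 and 22.6 months after 3/1/2021, a gap of 6.5 months before rounding. That is the widest gap of any pair. Without transplant the widest is 4.5 months.

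**What the listed fields cannot recover.** A tranche 1 patient may have had surgery in March 2021 or more than two years later. Under constant accrual, procedure type alone explains 4-5% of the variance in surgery date, and the full procedure-by-location cell explains 22-23%. The rest needs the date itself.

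**Direction.** For a practice in tranche k, the mean calendar step is (k + 5)/2 and the mean step since go-live is (7 − k)/2 (first step = 1). The two always sum to 6, so any gap in one is matched by an equal and opposite gap in the other.
- Calendar step: C-section (3×15 + 9)/17 = 3.18; transplant (2×12 + 5)/7 = 4.14. C-section is 0.97 earlier.
- Step since go-live: C-section (3×15 + 3)/17 = 2.82; transplant (2×6 + 1)/7 = 1.86. C-section is 0.97 later.

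**Illustrations, with trends that the documents do not give.** Suppose true engagement is the same in all procedure types.
- 30% in steps 1-2 and 50% afterwards: C-section (6×30 + 11×50)/17 = 42.9%, lung (2×30 + 10×50)/12 = 46.7%, transplant 50.0%. The spurious gaps from C-section are 3.7 points (lung) and 7.1 points (transplant).
- A calendar rise of 5 to 10 points per step: 0.97 × 5 = 4.8 to 0.97 × 10 = 9.7 points between C-section and transplant.
- The same rise per step since go-live and no calendar trend: the same size with the opposite sign.
- Both rises, equal: they cancel to zero.

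**The case against.** The strongest reply is that this is detail for a statistical analysis plan. Aim 1 is exploratory, leaves adjustment open and excludes no covariate. The printed list also cannot be the whole dataset: the pain and function outcomes are not on it, so trial data must be joined. Limiting the reports to patients who have finished follow-up already presupposes a surgery date. All of this stands, and it lowers the priority. It does not remove the point, because the Protocol presents the list as all the key variables and ties adjustment to what that process shows. A date used to select patients is not thereby kept for analysis.

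Several stronger readings are tempting, and the documents do not support them.
- *The rollout step is wholly lost.* Tranche and go-live date follow from listed fields. Only timing within a practice is missing.
- *Procedure types come from different eras.* Five of the seven start at step 1, and Figure 1 shows none stopping. Transplant stands out, lung less so, and the others overlap more.
- *The intervention was changed along the way.* The text says only that improvements may be identified and findings may be used.
- *The gender comparison is distorted too.* Ortho has a larger early share (29%) than gyn (26%), and the sex mix is not given. C-section plus gyn has 11/36 = 31% early time against 13/67 = 19% elsewhere. Under the 30%-to-50% jump that is about 2.2 points even if every other patient were male. This is too weak to raise.

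**Conclusion.** The point holds in a limited form. The Aim 1 variable list, presented as complete, lacks the field needed to separate procedure type from rollout timing. The uneven spread follows from Figure 1. The shares of 35% and 0% rest on equal volume per practice and a 7-month fifth step.

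The size and direction of any bias are unknown. A reader might take the 5 to 10 points as an estimate of the error, but they assume a calendar trend alone. Time since go-live pulls the other way and could cancel it. The comparisons at risk are chiefly those with transplant and, to a lesser degree, lung. For an exploratory aim this is a cheap improvement of modest priority.

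**What to change.** Add surgery date to the Aim 1 Epic report. Derive calendar step and months since the practice's go-live from it with Figure 1. Adjust for or stratify by both in the procedure-type comparisons and in the engagement-outcome correlation.

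As a check, repeat each procedure comparison in steps where all the compared types are active: from step 2 for lung and from step 3 for transplant. This check supplements the adjustment and does not replace it. In steps 3-5 the mean calendar steps of C-section and transplant nearly agree, (3×12 + 9)/11 = 4.09 against 4.14. The gap in steps since go-live widens, (3×12 + 3)/11 = 3.55 against 1.86.

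The cost is one date field that Epic already holds, two covariates, and slightly wider intervals for types concentrated in few steps, such as transplant with three practices in two tranches.
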